7.1.1.3 Patient demographics and other baseline characteristics

Data to be collected on patient characteristics at screening include:

- Demography (including: date of birth, age, patient initials, gender, childbearing potential, race and ethnicity, or as allowed by local regulations)
- Relevant medical history including: smoking history, previous cardiovascular and thromboembolic events. Any history of previous pre malignant or malignant cutaneous lesions should be collected.
- PV diagnosis and extent of disease, including:
 - Date of diagnosis
 - Estimated number of phlebotomies in the past 52 weeks
 - Prior antineoplastic therapies including use of hydroxyurea
- Prior and Concomitant Medications, surgical and medical procedures

All medications taken from screening must be recorded on the Prior and Concomitant medication eCRF page and updated on a continual basis if there is a new change to the medication.

7.1.2 Treatment period

Following completion of screening procedures and verifying patient eligibility, the patient will be approved for treatment via the IRT.

The study treatment phase begins on Day 1 with the first administration of ruxolitinib and will continue until disease progression (see [Appendix 4](#) and [Appendix 5](#)), unacceptable toxicity, death, withdrawal of consent for protocol specified procedures, or discontinuation from the study for any other reason until the drug becomes commercially available in each participating country.

Patients will be assessed as per visit schedule in [Table 7-1](#).

Visit windows of \pm 7 days from scheduled study assessments will apply up to Week 24 and \pm 14 days for visits after Week 24.

7.1.3 End of treatment visit including study completion and premature withdrawal

At the time patients discontinue study treatments, a visit should be scheduled as soon as possible, at which time all of the assessments listed for the End of Treatment (EOT) visit will

be performed and an End of treatment CRF page will be completed giving the date and reason for stopping treatment.

At a minimum, all patients who discontinue treatment, including those who refuse to return for a final visit, will be contacted for safety evaluations 30 days following the last dose of treatment by phone.

Patients who discontinue treatment should be considered withdrawn after the final visit assessments are performed or when it is clear that the patient will not return for these assessments.

If a withdrawal occurs, or if the patient fails to return for visits, the investigator must determine the primary reason for a patient's premature withdrawal from the study and record this information on the study Evaluation Completion CRF page.

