2.4.5 Date of first/last administration of study drug

The start date of study drug is defined as the first date when a non-zero dose of study drug was administered and recorded on the Dosage Administration Record (DAR) eCRF.

The date of last administration of study drug is defined as the last date when a non-zero dose of study drug was administered and recorded on DAR eCRF.

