2.8 Safety evaluation

The overall observation period will be divided into mutually exclusive segments:

We have

1. pre-treatment period: from day of patient's informed consent to the day before first dose of study medication
2. on-treatment period: from day of first dose of study medication to 30 days after last dose of study medication
3. If applicable, post-treatment period: starting at day 31 after last dose of study medication.

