4.4.5 Incomplete dates for last dose of INC424

Scenario 1

If the last date of study drug is after the cut-off date or is completely missing and there is no end of treatment eCRF page and no death date the patient should be considered to be on-going and use the cutoff date for the analysis as the last dosing date

Scenario 2

If the last date of study drug is completely or partially missing and there is EITHER an end of treatment eCRF page OR a death date available then imputed last dose date:

- = 31DECYYYY, if only Year is available and Year < Year of min (EOT visit date, death date)
- = Last day of the month, if both Year and Month are available and Year = Year of min (EOT visit date, death date) and Month < the month of min (EOT visit date, death date)
- = min (EOT visit date, death date), for all other cases

The imputed date will be compared with start date of study drug.

If the imputed date < start date of study drug, then last date of study drug is set to start date of study drug; otherwise, use the imputed date.

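### A missing last-dose date is imputed to the EOT visit or death date, passing over the treatment stop date that the End of Treatment page records

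*Protocol*

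**What the plan says.** - **Protocol 7.1.3.** On discontinuation "a visit should be scheduled as soon as possible", with no upper limit on the delay. The EOT assessments are done at that visit, and "an End of treatment CRF page will be completed giving the date and reason for stopping treatment". The section also foresees patients who do not attend: the 30-day safety call covers everyone who stops, "including those who refuse to return for a final visit".
- **SAP 2.4.5.** "The date of last administration of study drug is defined as the last date when a non-zero dose of study drug was administered", as recorded on the Dosage Administration Record (DAR) eCRF.
- **SAP 4.4.5, Scenario 2.** This applies when the DAR date "is completely or partially missing and there is EITHER an end of treatment eCRF page OR a death date available". There are two partial-date cases. A year alone, earlier than the year of the EOT visit or death, gives "31DECYYYY, if only Year is available". A known month in the same year, earlier than the month of the EOT visit or death, gives the end of that month. The remaining rule is "min (EOT visit date, death date), for all other cases". The result is never allowed to fall before the start of study drug.
- **SAP 2.8.** "on-treatment period: from day of first dose of study medication to 30 days after last dose of study medication".

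The same date also sets duration of exposure (SAP 2.4.6.1). Through the window and the patient-years it feeds the on-treatment deaths, the treatment-emergent events and the exposure-adjusted SAE and safety-event-category summaries (SAP 2.8.1). SAP 2.4.1 takes the reason for ending treatment from the End of Treatment disposition page. No section of the SAP uses a stop date from that page.

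**The concern.** The protocol distinguishes the date treatment stopped from the date of the visit arranged because it stopped. When the DAR date is missing, the first of these is the natural substitute. The SAP uses the page that should hold it only as a trigger, and then imputes from the visit or the death.

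If no drug is taken after the EOT visit, that choice is either exact or late. A late date lengthens exposure and extends the on-treatment window. Safety is the primary objective and the study has one arm, so the split between on-treatment and post-treatment events is a main result. A single death that changes column would be noticed.

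**Working it through.** The plan has no figure of its own to reproduce: the sample size of about 500 has no statistical basis and no hypothesis is tested. The check applies the Scenario 2 rule as written to constructed dates. All dates, gaps and missing rates below are assumptions.

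**1. Size of the error for one patient.** Let F be the first dose, L the true last dose, V = L + g the EOT visit and D the death date, with the DAR last-dose date wholly missing.

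- Imputed last dose: L* = min(V, D). If V is not after D, L* = L + g.
- Exposure error: (L* − F + 1) − (L − F + 1) = g days.
- End of window: L* + 30 = L + (30 + g).
- An event d days after L, with d > 30, becomes on-treatment when d ≤ 30 + g, that is, when g ≥ d − 30.

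**2. Numbers.** F = 11 Jan 2016 and L = 1 Sep 2016, so true exposure is 235 days. Death is 45 days after L, which is post-treatment on the true dates.

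| Gap g (days) | Exposure used (days) | Window ends, days after L | Death on day 45 counted as |
|---|---|---|---|
| 0 | 235 | 30 | post-treatment |
| 7 | 242 | 37 | post-treatment |
| 14 | 249 | 44 | post-treatment |
| 15 | 250 | 45 | on-treatment |
| 21 | 256 | 51 | on-treatment |
| 28 | 263 | 58 | on-treatment |

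The switch comes at g = 45 − 30 = 15.

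**3. Partial dates left to the remaining rule.** Suppose the last dose is known to be in November 2016 (true date 5 November) and the EOT visit is on 16 January 2017. The month-end case requires the same year, so it does not apply and the imputed date is 16 January 2017. That is 72 days late and 47 days past the end of a month that was known.

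**4. Size in the cohort.** Excess patient-years = 500 × p × g / 365.25, where p is the proportion with a missing date.

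- p = 1%, g = 7: 500 × 0.01 × 7 / 365.25 = 0.10, or 0.02% of an assumed 500 patient-years.
- p = 5%, g = 28: 500 × 0.05 × 28 / 365.25 = 1.92, or 0.38%.
- p = 10%, g = 84: 500 × 0.10 × 84 / 365.25 = 11.5, or 2.3%.

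If total exposure were 250 or 1,000 patient-years instead of 500, the last figure would be 4.6% or 1.15%.

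**5. Exposure-adjusted rates.** The extra days enter the denominator, and events drawn into the longer window enter the numerator. The net direction is not fixed. In relative dose intensity (SAP 2.4.6.1) the duration appears in both actual and planned intensity and cancels, so it can change only through the cumulative doses.

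**6. With the recorded stop date used first.** Where that date equals L, the excess is 0 days in every row above and the death on day 45 stays post-treatment.

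**The case against.** The case for leaving the rule alone has several parts.

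- **The CRF is not among the documents.** The SAP does not define the EOT visit date or list the fields on the End of Treatment page. The sponsor may have meant the stop date on that page. This stands as a caveat: the SAP wording would then still need correcting, but the derivation would not.
- **The trigger is narrow.** Doses and dose changes go on the DAR, missing values are queried before lock (Protocol 9.4), and the follow-up call is timed from the last dose. This stands, and is why the cohort effect is probably small.
- **The gap may be zero.** SAP 4.3.1 provides for patients who start and discontinue on the same day, with EOT data from that day. The protocol glossary also allows discontinuation after a final visit, so the claim that the error is never early depends on no dosing after the EOT visit. A long gap is nevertheless possible: SAP 2.8.1 notes discontinuation after AE interruptions of more than 8 weeks, so a last non-zero dose could precede the visit by over 56 days.
- **Few late events are there to move.** AE monitoring is required for at least 30 days after the last dose (Protocol 8.1.1), and later SAEs are reported only if a causal relationship is suspected (Protocol 8.2.2). All deaths are tabulated and listed as well as on-treatment deaths, so none disappears. This limits the harm but does not make the on-treatment column correct.

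A reader might also take the patient who refuses the final visit and dies months later as the clearest proof, since the minimum would presumably then be the death date itself. The documents do not support using that case. Protocol 7.1.3 has the page completed at the visit and does not say that a patient who refuses still has a page with a stop date. Without one, the proposed rule falls back to the same imputed date.

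**Conclusion.** The point holds for patients whose DAR last-dose date is wholly missing, or partial and left to the remaining rule, and who have an End of Treatment page with a stop date. If the EOT visit follows the stop by g days, the imputed last dose is g days late, exposure is g days too long, and the on-treatment window runs to 30 + g days after the true last dose. This assumes that the recorded stop date is at or near the last dose and that no drug is taken after the visit.

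The number of such patients is not given. On the assumed ranges the excess is about 0.02% to 2.3% of 500 patient-years, and the top of that range needs both 10% missing and 84-day gaps. The cohort effect is therefore probably small. The practical risk is that one or a few deaths or adverse events are placed in the wrong period.

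Two stronger conclusions might be inferred and are not supported. One is that exposure-adjusted rates are biased in a known direction; numerator and denominator can both rise. The other is that large percentage errors in exposure are typical; such figures come from single patients with short exposure and chosen dates. The correction is still worth making, because it replaces a proxy with a date the protocol says is recorded.

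**What to change.** Amend SAP 4.4.5 Scenario 2 as follows:

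1. If the last-dose date is missing or partial and the End of Treatment page gives a treatment stop date, use that date. Cap it at the death date and keep it consistent with any known month or year of the last dose.
2. Use the earlier of EOT visit and death only when no stop date is recorded. This may include patients who refused the final visit.
3. Flag deaths whose on-treatment status rests on an imputed last-dose date.
4. If the EOT visit date was intended to mean the stop date on that page, correct the wording to say so.

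The cost is one added derivation step and a flag; on the protocol's account the date is already collected. The drawback is that the recorded stop date may be the date of the decision, slightly later than the last dose taken, so a small overstatement can remain.

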7.1.3.1 Criteria for premature patient withdrawal

Patients may voluntarily withdraw from the ETP at any time.

Patient death will be considered as a withdrawal from the study. Patients may also be withdrawn (the physician may decide to remove the patient from any further study activity) if any of the following occur:

- Adverse event(s) (see [Section 8.1](#))
- Major protocol deviation
- Technical problems
- Physician decision
- Non-compliance with study treatment

Patients must be withdrawn if any of the following occur:

- Lost to follow-up
- Patient/guardian decision
- Study terminated by sponsor
- Pregnancy (Pregnancy will be followed for outcome)
- Disease progression – sites should indicate type of progression and include information on the diagnostic bone marrow biopsy result if obtained as per diagnostic criteria (see [Appendix 4](#) and [Appendix 5](#)).
- Withdrawal of consent

Patients lost to follow up should be recorded as such on the eCRF. For patients who are lost to follow-up, the investigator should show "due diligence" by documenting in the source documents steps taken to contact the patient, e.g. dates of telephone calls, registered letters, etc.

Treatment duration is considered "completed" three months after the expanded treatment plan's drug becomes commercially available for the PV indication in the patients participating country or by 31 Dec 2017, whichever comes first, and the patient should be transitioned to commercial product. Study sites should stop all patients' study participation on the study at this time.

7.1.3.2 Replacement policy

Patients will not be replaced on study

7.1.4 Follow up period

All patients must have a follow up safety phone evaluation 30 days after the last dose of treatment (Study Evaluation Completion or EoS).

Patients lost to follow up should be recorded as such on the CRF. For patients who are lost to follow-up, the investigator should show "due diligence" by documenting in the source documents steps taken to contact the patient, e.g., dates of telephone calls, registered letters, etc.

7.2 Assessment types

7.2.1 Efficacy assessments

Assessments for efficacy will consist of Hct measured locally, spleen by palpation, and MPN-SAF TSS.

- Samples for hematology assessments will be prepared and analyzed locally as indicated in [Table 7-1](#). Data for specific Hematology tests will be recorded in the eCRF as indicated in [Table 7-2](#).

7.2.2 Safety and tolerability assessments

Safety will be monitored by the assessments described below as well as the collection of AEs at every visit. For details on AE collection and reporting, refer to. Significant findings that were present prior to the signing of informed consent must be included in the relevant medical history/current medical conditions page on the patient's eCRF. Significant new findings that begin or worsen after informed consent must be recorded on the Adverse Event page of the patient's eCRF.

7.2.2.1 Physical examination

Physical examinations will include an examination of general appearance, skin, neck (including thyroid), eyes, ears, nose, throat, lungs, heart, abdomen, back, lymph nodes, extremities, and a basic nervous system evaluation. Information about the physical examination must be present in the source documentation at the center. For the assessment schedule refer to [Table 7-1](#).

Spleen will be assessed by palpation at visits indicated in [Table 7-1](#). If palpable, a soft ruler should be used to document the spleen size, rounded to the nearest centimeter, from the left costal margin to the point of greatest splenic protrusion. Spleen size will be used to determine if dose increases for lack of efficacy should be considered at or subsequent to Week 4 and for routine patient management. Spleen length information will be documented in the eCRF.

Significant findings that were present prior to the signing of informed consent must be included in the Medical History page on the patient's CRF. Significant new findings that

begin or worsen after informed consent must be recorded on the Adverse Event page of the patient's CRF except for spleen length which will be documented in a separate eCRF page.

7.2.2.2 Vital signs

Vital signs include body temperature and blood pressure. Blood pressure (systolic and diastolic) should be measured after the patient has been sitting for five minutes.

For the assessment schedule refer to [Table 7-1](#)

7.2.2.3 Height and weight

Height in centimeters (cm) will only be collected at screening. Body weight (to the nearest 0.1 kilogram (kg) with indoor clothing on, but without shoes) will be measured at every study visit.

7.2.2.4 Performance status

The performance status will be assessed per the schedule in [Table 7-1](#) and according to the ECOG performance status scale (see [Appendix 2](#)).

7.2.2.5 Laboratory evaluations

Local site laboratories will be used for the analysis of scheduled hematology, biochemistry, urine, and other blood specimens collected as part of safety monitoring. All unscheduled blood testing will be performed locally. The time windows granted for laboratory evaluations are identical to the corresponding visit time windows for each visit (refer to [Section 7.1](#))

Laboratory abnormalities that are considered clinically significant, induce clinical signs or symptoms, require concomitant therapy or require changes in ruxolitinib treatment (see [Section 8.1](#)) constitute an adverse event (AE) and must be reported as an AE on the AE CRF page.

Laboratory values obtained at the screening visit will be used to assess eligibility to meet inclusion criteria. If patient meets all inclusion and no exclusion criteria, the screening labs can be used for baseline if patient is dosed within 14 days of the screening visit. If patient cannot be dosed within 14 days of screen, then the labs should be repeated the day before patient starts dosing (see baseline visit in [Table 7-1](#)).

Only Hematocrit (Hct), Hemoglobin (Hb), Platelet (Plt), White Blood Count (WBC), absolute or % neutrophils and pregnancy values will be collected on the eCRF.

Table 7-2 Local clinical laboratory parameters

| Test Category | Documentation | Test Name |
|---------------|------------------|---|
| Hematology | eCRF | Hematocrit, Hemoglobin, Platelets, WBC, Absolute or % Neutrophils |
| Hematology | Source documents | Hematocrit, Hemoglobin, Mean Corpuscular Hemoglobin (MCH) , Mean Corpuscular Hemoglobin Concentration (MCHC), Mean Corpuscular Volume (MCV), Platelets, Red blood cells, White blood cells, %Blasts, Red Blood Count (RBC), White Blood Cells with Differential (Basophils, Eosinophils, Lymphocytes, Monocytes, Neutrophils) |

| Test Category | Documentation | Test Name |
|---------------|------------------|---|
| Chemistry | Source Documents | Albumin, Alkaline phosphatase, ALT (SGPT), AST (SGOT), Bicarbonate, Calcium, Chloride, Creatinine, Creatine kinase, Direct Bilirubin, Indirect Bilirubin, Total Bilirubin, Total Cholesterol, Low Density Lipoprotein (LDL), High Density Lipoprotein (HDL), Total Protein, Triglycerides, Blood Urea Nitrogen (BUN) or Urea, Uric Acid |
| Urinalysis | Source Documents | Macroscopic Panel (Dipstick) (Color, Bilirubin, Blood, Glucose, Ketones, Leukocytes esterase, Nitrite, pH, Protein, Specific Gravity, Urobilinogen) |
| Coagulation | Source Documents | Prothrombin time (PT) or International normalized ratio [INR]), Partial thromboplastin time (PTT), Activated partial thromboplastin time (APTT) |
| Pregnancy | eCRF | Serum at screening and End of Treatment (EOT); Urine - all other time points |

7.2.2.5.1 Pregnancy and assessments of fertility

All pre-menopausal women who are not surgically sterile will have a serum hCG test at screening. Thereafter, the patients will have a urine pregnancy test. At the End of Treatment visit a serum hCG test will be done. A positive urine pregnancy test requires immediate interruption of study drug until serum hCG is performed and found to be negative. If positive, the patient must be discontinued from the study. All the urine pregnancy tests will be performed locally. See [Section 5.3](#) for further information on required birth control methods.

The time windows granted for pregnancy testing are identical to the corresponding visit time windows for each visit. Refer to [Table 7-1](#). If local requirements dictate otherwise, local regulations should be followed.

If a positive pregnancy test is performed in between visits, the patients must immediately notify the investigator.

7.2.2.6 Cardiac assessments

Not applicable.

7.2.3 Biomarkers

Not applicable.

7.2.4 Resource utilization

Not applicable.

7.2.5 Patient reported outcomes

Patient reported Outcomes will be collected through the MPN-SAF according to the Visit Schedule outlined in [Table 7-1](#).

The patient should be given sufficient space and time to complete the questionnaire. The site personnel should check the questionnaire for completeness and ask the patient to complete any missing responses. The original questionnaire will be kept with the patient's file as the source document.

Completed questionnaire(s) and any unsolicited comments written by the patient should be reviewed and assessed by the investigator for responses which may indicate potential AEs or SAEs before any clinical study examinations. This assessment should be documented in study source records. If AEs or SAEs are confirmed, study investigators should not encourage the patient to change responses reported in the completed questionnaires. Study investigators must follow reporting instructions outlined in [Section 8](#) (e.g. reference “Adverse Events” section) of the study protocol.

MPN-SAF

The MPN-SAF ([Appendix 6](#)) is a disease specific questionnaire comprised of 10 items that measures fatigue related to MPN disease and the severity of nine of the most prevalent associated symptoms including: early satiety, abdominal discomfort, inactivity, concentration, night sweats, itching, bone pain, fever and weight loss. There are three recall periods used in this questionnaire, they are 24 hours for fatigue, the past week for symptoms of early satiety, abdominal discomfort, inactivity, concentration, night sweats, itching, bone pain and fever, and the past 6 months for weight loss. Each item is scored on a scale ranging from 0 (no fatigue/absent) to 10 (As bad as you can imagine/worst imaginable). The MPN-SAF TSS is computed as the average of the observed items multiplied by 10 to achieve a 0-to-100 scale. The MPN-SAF TSS thus has a possible score range of 0 to 100.

8 Safety monitoring and reporting

